### 9.3.5 Analysis of exploratory endpoints

#### Exploratory endpoints

- Efficacy of two doses of Ad5-nCoV in preventing symptomatic disease of COVID-19 (confirmed by PCR) occurring 14 and 28 days to 52 weeks after vaccination, regardless of severity.
- Efficacy of two doses of Ad5-nCoV in preventing virologically (PCR) or serologically (four-fold increase in SARS-CoV-2 anti-N IgG from pre-immunization to post symptom, defined as Day 21-28 post illness blood test, or pre-symptom to post-symptom blood test) confirmed COVID-19 disease occurring 14 and 28 days to 52 weeks after vaccination, regardless of severity.
- Efficacy of two doses of Ad5-nCoV in preventing severe COVID-19 disease caused by SARS-CoV-2 infection from 14 and 28 days to 24 and 52 weeks after vaccination.
- Efficacy of two doses of Ad5-nCoV in preventing asymptomatic disease of COVID-19 (confirmed by N IgG antibody on week 52 after vaccination).
- Severity of COVID-19 cases among vaccine recipients (based on WHO or FDA criteria) as compared to the control group, to measure antibody-mediated disease enhancement (ADE).
- SARS-CoV-2 virus shedding in COVID-19 cases that occurred 28 days to 52 weeks after vaccination (detection of viral nucleic acid every 2 days after being confirmed).
- Genotype of SARS-CoV-2 virus isolates of COVID-19 cases that occurred 28 days to 52 weeks after vaccination.
- Suspected but unconfirmed cases of COVID-19 (either because of negative or no tests).
- Evaluate incidence of suspected but unconfirmed cases of COVID-19 (either because of negative or no tests).

Analysis of endpoints will be descriptive. PCR confirmed positive subjects will be classified as having severe or non-severe disease. Severity of disease, SARS-CoV-2 virus shedding and Genotypes SARS-CoV-2 virus isolates will be listed by subject and date, along with demographic data, including the study centre. Suspected but unconfirmed cases and asymptomatic cases will also be listed.

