##### **Confirmed case**

A suspect case with laboratory confirmation of COVID-19 infection (including PCR positive result OR 4 folds or greater increase of anti N IgG at 4 folds or more raise between convalescence phase as compared to an acute phase), irrespective of clinical signs and symptoms.

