##### **Endpoint case**

Confirmed cases are categorized into primary endpoint cases and secondary endpoint cases according to the time of onset after vaccination.

Primary endpoint: the participant with clinical symptom(s) that occurred not less than Confirmed cases with onset date  $\geq 28$  days after post- vaccination and the PCR test is positive.

Secondary endpoint: the participant with clinical symptom(s) that occurred not less than 14 days post-vaccination and the PCR test is positive; or 4 folds or greater increase of anti N IgG is detected after the occurrence of the clinical symptom(s).

Confirmed cases with onset date  $\geq 28$  days after vaccination.

Both primary and secondary endpoint cases need to be reported to the Endpoint Review Committee (ERC) for final review. A contact is a person who experienced any one of the following exposures during the 2 days before and the 14 days after the onset of symptoms of a probable or confirmed case:

1. Face-to-face contact with a probable or confirmed case within 1 meter and for more than 15 minutes;
2. Direct physical contact with a probable or confirmed case;
3. Direct care for a patient with probable or confirmed COVID-19 disease without using proper personal protective equipment;

OR

4. Other situations as indicated by local risk assessments.

*Note: for confirmed asymptomatic cases, the period of contact is measured as the 2 days before through the 14 days after the date on which the sample was taken which led to confirmation.*

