## **12.2 Endpoint Review Committee**

The Endpoint Review Committee (ERC) will be blinded to the treatment assignments. Each endpoint case will be reviewed independently by two ERC members to confirm endpoint and severity; if their adjudications conflict, the endpoint will also be reviewed by a third member and the endpoint will be adjudicated by the majority vote. Members of the ERC will be appointed by the Study Steering Committee. Each positive laboratory result will be reviewed by the ERC. A detailed outline of ERC regulations and endpoint case criteria, in addition to the criteria defined below, will be available in the ERC charter.

Endpoints cases are defined by any of the following events:

1. A participant has an illness visit and virological confirmation (positive PCR test). PCR SARS-CoV-2 tests are permitted to be carried out at local study sites. Every effort will be made to verify positive PCR tests in a central reference laboratory.
2. A participant has an illness visit and serological confirmation of SARS-CoV-2. A positive serology test is defined by a four-fold rise or greater to N antibody titers in association with the illness.
3. A participant has illness visit and both virological and serological confirmation.
4. A participant who does not present with any symptoms (does not have any illness visits) but demonstrates seroconversion to the N antigen between the Injection and Week 52 visits.

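### Serological confirmation of COVID-19 uses a different reference sample in the exploratory endpoint than in the confirmed-case definition, so a silent infection after baseline can turn a later unrelated illness into a counted symptomatic case

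*Protocol*

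**What the plan says.** The serological criterion appears in four forms in the Protocol.

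- **Exploratory endpoint** (9.3.5; same rule in both exploratory lists of the synopsis and in 2.2.4). Two routes are joined by *or*. The first is a "four-fold increase in SARS-CoV-2 anti-N IgG from pre-immunization to post symptom, defined as Day 21-28 post illness blood test". The sentence continues "or pre-symptom to post-symptom blood test) confirmed COVID-19 disease occurring 14 and 28 days to 52 weeks after vaccination".
- **Confirmed case** (3.5). Apart from PCR, confirmation needs "4 folds or more raise between convalescence phase as compared to an acute phase". There is no route from the pre-immunization sample.
- **Endpoint case** (3.5). The secondary endpoint case counts when "4 folds or greater increase of anti N IgG is detected after the occurrence of the clinical symptom(s"). No reference sample is named.
- **Endpoint Review Committee** (12.2). The requirement is a "four-fold rise or greater to N antibody titers in association with the illness". Again no reference sample is named. A separate category covers a participant without any illness visit who "demonstrates seroconversion to the N antigen between the Injection and Week 52 visits".

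Three other provisions matter. Under 3.5, a single symptom from a broad list makes a suspected case, and every suspected case gives serum at presentation and again three to four weeks later, whatever the PCR result. Under 3.2 and 5.1, former placebo recipients keep their first-visit serology as baseline, and Table 2 shows no antibody sample at Visit 1.B. Under 9.3.5, the exploratory endpoints are analysed descriptively.

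**The concern.** The reference sample decides what a four-fold rise means. A rise between two sera taken around one illness points to an infection at about that time. A rise since the pre-immunization sample shows only that infection happened at some point since then, possibly months before the illness.

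Two sections therefore fix two different rules, and the same participant can be a case under 9.3.5 and not under 3.5. This is not detail left for an analysis plan, because both rules are stated. At stake is who enters the count of PCR- or serologically confirmed symptomatic disease. The asymptomatic category is affected too: a silently infected person who later attends for an unrelated complaint no longer meets the no-illness-visit condition in 12.2, and can reappear as a symptomatic case.

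**Working it through.** The Protocol gives no expected count, power or sample size for this endpoint, so there is no figure to reproduce. The check has three steps.

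**1. The rules applied to titre patterns** (illustrative anti-N values: baseline / acute / convalescent)

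| Pattern | Convalescent ÷ baseline | Convalescent ÷ acute | 9.3.5, pre-immunization route | 3.5, confirmed case |
|---|---|---|---|---|
| 10 / 10 / 80, infection causes the illness | 8.0 | 8.0 | case | case |
| 10 / 80 / 80, silent infection, later unrelated illness | 8.0 | 1.0 | case | not a case |
| 10 / 80 / 60, the same with some waning | 6.0 | 0.75 | case | not a case |
| 80 / 80 / 80, infection before the baseline sample | 1.0 | 1.0 | not a case | not a case |

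The rules disagree for silent infections after baseline and agree for infections before it. The second pattern would also fit a true case who presents late, with anti-N already raised. The paired sera cannot separate the two.

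**2. Possible size.** Inputs: N = 500 (3.2). Everything else is assumed: 15% annual infection risk, 40% of infections silent, infection times uniform over one year, unrelated illness visits Poisson with rate L per year, anti-N always still at least four-fold raised, and no committee rejection.

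Infections: 500 × 0.15 = 75, of which 75 × 0.40 = 30 are silent and 45 symptomatic.

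Share of silent infections followed by at least one unrelated visit: 1 − (1 − e^(−L)) / L.

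| L | Share | Extra cases (30 × share) | Relative to 45 |
|---|---|---|---|
| 1 | 0.368 | 11.0 | 24.5% |
| 2 | 0.568 | 17.0 | 38% |
| 3 | 0.683 | 20.5 | 46% |

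Over a wider assumed range (silent-infection risk 5% to 20%, L from 0.5 to 2, persistence 50% to 100%), the same formula gives about 3 to 57 participants in 500.

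**3. Under an acute-to-convalescent rule.** Suppose an unrelated illness within 28 days of a silent infection still shows a rise. The residual is then 30 × (1 − e^(−28L/365)) = 2.2, 4.3 and 6.2 for L = 1, 2, 3. Over the wider range it is about 0.5 to 14.

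**Former placebo recipients.** Their reference serum predates the first active dose by the length of the blinded period, which the Protocol does not state. An infection in that period also counts as a rise from baseline, so their exposure to this error is the longest.

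**The case against.** The strongest defence is that the case process would catch the error. Section 3.5 draws endpoint cases from confirmed cases, which need an acute-to-convalescent rise. Every endpoint case goes to the committee, and 12.2 ties the rise to the illness, judged by two independent members who could have a flat serum pair before them. Further criteria sit in a charter that is not available here. This limits the damage but does not remove the contradiction. Section 9.3.5 states its own rule without reference to 3.5, and 12.2 gives the committee no reference sample to apply.

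Four stronger readings are tempting and are not supported.

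- *The endpoint measures the rise only from the pre-immunization sample.* It does not; the pre-symptom route stands beside it. But because the routes are alternatives, the second does not remove the fault of the first.
- *Any old infection turns any later illness into a case.* The infection must follow the baseline sample, anti-N must still be four-fold raised at Day 21-28, onset must fall in the window, and the committee must accept the case.
- *The reference sample decides the onset date, and so the 14- or 28-day window.* Onset is taken from the symptoms under either rule; the reference sample decides only whether the illness is a case.
- *The count is inflated by a known 24% to 46%.* Persistence and committee acceptance were set at their extremes, so these are upper bounds for rates that are themselves assumed.

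The consequence is also modest. The study is open and non-comparative, 9.3.2 tests no efficacy hypothesis, and the PCR-only endpoint and the PCR-based primary endpoint case are untouched.

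**Conclusion.** The contradiction is in the text and needs correcting. The pre-immunization route can count a silent infection plus a later unrelated illness as serologically confirmed symptomatic COVID-19, while the confirmed-case definition would not. On the stated assumptions this adds at most about 11 to 20 cases beside about 45 true ones in 500. The direction follows from the definitions; the size rests wholly on assumed rates. It reaches one exploratory, descriptive count and the asymptomatic category, and no primary objective, error rate or power statement. It is worth fixing because the rule as written gives a wrong answer and the correction is cheap.

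**What to change.** State one rule in the synopsis, 2.2.4, 3.5 (confirmed case and endpoint case), 9.3.5 and 12.2: serological confirmation is a four-fold or greater anti-N rise from the illness-presentation serum to the Day 21-28 serum. List a rise shown only against the pre-immunization serum or an earlier scheduled serum separately as *infection, timing unknown*, including when the presentation serum is missing or already raised. Do not count it as a serologically confirmed symptomatic case.

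Do not add a fallback to the last scheduled serum when the presentation serum is already raised. In the problem cases it nearly always is, and no serum is scheduled between Week 24 and Week 52. With sera at Days 0, 28, 84, 168 and 364, extra cases are 30 × Σ[d − (1 − e^(−Ld)) / L], where d is each gap (28, 56, 84 and 196 days) divided by 364. This gives 4.8, 8.5 and 11.2 for L = 1, 2, 3, so 44% to 55% of the error would remain.

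At the same time, reconcile the convalescent timing in 5.1 (illness visits), which gives both two to three weeks and 21 to 28 days.

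The cost is wording only, since both sera are already planned for every suspected case. The downside is that some true PCR-negative cases who present late move to the unknown-timing list, where they stay visible.

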## 10. DATA MANAGEMENT

### 10.1 General Requirements

The data management of this clinical trial will follow the CDISC standard. A designated person (Central Data Manager) will be responsible for the data management of global clinical trial and develop a core data management plan approved by the global PI and the sponsor. The local PI of each participating country along with the Sponsor will identify a local CRO to monitor data entry and ensure compliance with the CDISC standard.

## 10.2 Electronic Data Capture System

This clinical trial will use a single, designated Electronic Data Capture System (EDC) in all participating countries. The local PI of each country must ensure that its research team is well trained in EDC system operation skills.

# 11. STUDY SUSPENSION CRITERIA AND SAFETY MONITORING

The study in its entirety may be terminated prematurely with reasonable justification by Study Steering Committee, National Regulatory Authority (ANMAT), or the Ethics Committee with oversight responsibilities at any time, and/or individual participants may terminate their participation prematurely, or have their participation be terminated by the Investigator.

An Independent Data Monitoring Committee (IDMC) will be established to review the safety data of every participant with a GRADE 4 adverse event. Meetings will also be held should a participant have an adverse event meeting a “holding rule”. The safety review will be conducted using blinded data. The efficacy review will use unblinded data, but interim reports will not disclose the data at least that IDMC suggest changes in the protocol due to efficacy concerns.

### 11.1 Study Suspension Criteria

If a suspension criterion is activated, the study will be put on hold, and further injections will not be administered until a safety review has been conducted. Should a suspension criterion be activated, the local PI will inform the global PI, Sponsors, and NRA within 24 hours.

Suspension criteria include:

- More than 15% of participants experience a Grade 3 AE beginning within 3 days after study injection (day of injection and 2 subsequent days) and persisting at Grade  $\geq 3$  on three consecutive days depending upon symptom severity and kinetics.
- A suspected, unexpected serious adverse reaction (SUSAR) occurs that is life-threatening or results in death.
- The IDMC assessed the potential safety risks in clinical studies.
- The IDMC assessed that the vaccine candidate might be ineffective.

### 11.2 Study Early Termination Criteria

- Required by the sponsor, or
- Required by the regulatory authority, or
- Required by an institutional review board (IRB)

### 11.3 Process of Suspension of Injection and/ or Study Modification

In the event that a safety signal is observed, the IDMC might decide to cancel injection of all groups (early termination of study) or selected groups.

In this case, for impacted groups:

- Participants who are already injected will continue all visits as planned.
- Participants who signed an informed consent but have not received any study product will be informed that their study participation will be stopped.

Details of the IDMC functioning are described in the IDMC Charter.

## 12. STUDY GOVERNANCE

The study will be managed by Fundación Huésped. It is Fundación Huésped responsibility to oversee all study site activities. There will also be a designated IDMC to continuously monitor and review data from safety and efficacy trial.

### 12.1 Study Steering Committee

A Study Steering Committee (SC) will be established by the sponsor as the management decision-making body for this clinical trial. The SC will provide guidance to Fundación Huésped who will be responsible to ensure that the conduct of the trial in each site is harmonized with respect to important aspects such as data collection, laboratory tests, and implementation of vaccination. Approval, revision, adaptive adjustment of the clinical trial protocol, and major issues such as suspension and termination of clinical trials will all be decided by SC.

The composition of SC is as follows:

- Representatives from the sponsor
- PI and co-Global co-PI
- Central Safety Physician
- Central Statistician

**The main responsibilities of PI and Global co-PI are:**

- Assisting the sponsor to formulate the clinical trial protocol.
- In the course of clinical trials, coordinating the progress of each clinical trial site, and making recommendations for adaptive adjustment according to changes in circumstances (e.g., COVID-19 attack rate).
- When necessary, working with country PI to resolve issues that arise in the course of clinical trials.
- Preparing study reports for clinical trial.
- Working with the Study Statistician to finalize the Statistical Analysis Plan (SAP)
- Drafting local implementation documents and informed consent form (ICF) based on the clinical trial protocol and ICF.

- Submission of protocol, ICF, and other study documentation to the local IRB.
- Conducting clinical trials based on the approved implementation protocol.
- Solving the problems that occurred during the clinical trial.
- Preparing study reports for the sub-center clinical trial.

## **12.2 Endpoint Review Committee**

The Endpoint Review Committee (ERC) will be blinded to the treatment assignments. Each endpoint case will be reviewed independently by two ERC members to confirm endpoint and severity; if their adjudications conflict, the endpoint will also be reviewed by a third member and the endpoint will be adjudicated by the majority vote. Members of the ERC will be appointed by the Study Steering Committee. Each positive laboratory result will be reviewed by the ERC. A detailed outline of ERC regulations and endpoint case criteria, in addition to the criteria defined below, will be available in the ERC charter.

Endpoints cases are defined by any of the following events:

1. A participant has an illness visit and virological confirmation (positive PCR test). PCR SARS-CoV-2 tests are permitted to be carried out at local study sites. Every effort will be made to verify positive PCR tests in a central reference laboratory.
2. A participant has an illness visit and serological confirmation of SARS-CoV-2. A positive serology test is defined by a four-fold rise or greater to N antibody titers in association with the illness.
3. A participant has illness visit and both virological and serological confirmation.
4. A participant who does not present with any symptoms (does not have any illness visits) but demonstrates seroconversion to the N antigen between the Injection and Week 52 visits.

## **12.3 Independent Data Monitoring Committee**

The sponsor will establish an Independent Data Monitoring Committee (IDMC) consisting of at least 3 members to review global clinical trial safety and efficacy data. The IDMC core members will include an independent safety physician, clinical trial experts, an independent expert physician, infectious disease clinicians, biostatisticians, and epidemiologists who are not otherwise involved in the conduct of the project.

IDMC's main responsibilities are:

- Reviewing the reported safety data in the participants after vaccination.
- Assessing the safety, if necessary, in the context of efficacy, of the investigational vaccine to safeguard the interests of trial participants.

- Conducting interim analysis and terminate the trial early (for benefit or futility) when sufficient evidence of efficacy is obtained.
- Monitoring the overall conduct of the clinical trial to protect its validity and credibility.

### **13. ETHICAL AND REGULATORY CONSIDERATIONS**

This study will be conducted in accordance with all regulatory requirements. The trial will be conducted in accordance with the latest version of the Declaration of Helsinki, GCP, ICH regulatory guidelines, and requirements regarding ethical committee review, informed consent, and other statutes and regulations regarding the protection of the rights and wellbeing of participants in the study.

Each enrolment site and local investigator will be responsible for submitting this protocol, the informed consent document, and all recruiting materials to their local independent Research Ethics Board (IRB) for review and approval.

No changes will be made to the protocol without IRB approval, except where necessary to eliminate apparent immediate hazards to participants.

Participants will be able to withdraw their consents to participate at any time without giving a reason and with assurance that their care will not be affected in any way. The investigators may withdraw a participant if, in the investigator's clinical judgment, it is in the best interest of the participant or if the participant is unable to comply with study requirements.

#### **13.1 Benefits/Potential Risks**

A complete description of the potential risks and benefits can be found in the informed consent document and Investigator Brochure [10].

#### **13.2 Informed Consent Process and Documentation**

The investigator or designate person will be responsible for presenting a full description of the research project including risks/benefits, and how personal health information may be used and disclosed in research. A written informed consent/authorization will then be obtained from the participant prior to the screening procedures and injection. The principal investigator or designate will also be responsible for maintaining up-to-date records of the consent forms and providing a copy to the participant.

Participants will be encouraged and will have ample opportunity to have their questions answered before and after consenting to participate.

#### **13.3 Modification of the Protocol**

No modifications of the protocol may be made by study personnel without consultation the principal investigator. Any protocol amendment will be submitted to the appropriate local regulatory authority and to the Research Ethics Board(s) for approval.

